2.3. Study Endpoints

2.3.1. Primary Endpoint

Overall response rate (ORR) at Day 28, defined as the proportion of subjects demonstrating a complete response (CR), very good partial response (VGPR), or partial response (PR).

2.3.2. Secondary Endpoints

Key secondary endpoint and other secondary endpoints are included in the following:

- Key secondary endpoint: Six-month duration of response (DOR), defined as the time from first response until GVHD progression or death. DOR will be assessed when all subjects complete the Day 180 visit.
- ORR, defined as the proportion of subjects demonstrating a CR, VGPR, or PR at Days 14, 56, and 100.
- Three-month DOR, defined as the time from first response until GVHD progression or death, when all subjects complete the Day 84 visit.
- Nonrelapse mortality (NRM), defined as the proportions of subjects who died due to causes other than malignancy relapse at Months 6, 9, 12, and 24.
- Relapse rate, defined as the proportion of subjects whose underlying malignancy relapses.
- Relapse-related mortality rate, defined as the proportion of subjects whose malignancy relapses and has a fatal outcome.
- Failure-free survival (FFS), defined as the proportion of subjects who are still alive, have not relapsed, have not required additional therapy for acute GVHD, and have not demonstrated signs or symptoms of chronic GVHD, at Month 6.
- Overall survival (OS), defined as the time from study enrollment (first day of ruxolitinib treatment) to death due to any cause.
- Summary of clinical safety data (eg, AEs, infections) will be tabulated and listed.
- Maximum observed plasma drug concentration (C_{max}), minimum observed plasma drug concentration (C_{min}), time of maximum observed plasma drug concentration (t_{max}), area under the plasma drug concentration versus time curve (AUC), and apparent clearance of study drug from plasma (CL/F).

3. STUDY DESIGN

This is an open-label, single-cohort, multicenter Phase 2 study of ruxolitinib in combination with corticosteroids for the treatment of steroid-refractory Grades II to IV acute GVHD. Eligible subjects will begin treatment at 5 mg twice daily (BID) ruxolitinib; if hematologic parameters are stable and no treatment-related toxicity is observed after the first 3 days of treatment, the dose may be increased to 10 mg BID. Ruxolitinib may be tapered after Day 180 provided the subject has achieved CR or VGPR and corticosteroids have been discontinued for at least 8 weeks. Corticosteroids will be administered at a starting dose of 2.0 mg/kg per day (unless otherwise indicated) on Day 1 and will be tapered as appropriate. Subjects will receive study treatment until treatment failure (progression of GVHD, no response, or requiring additional systemic therapy), unacceptable toxicity, or death. Continued use of anti-infective medications, GVHD prophylaxis medications (including calcineurin inhibitors), transfusion support, and topical steroid therapy is permitted.

Severity of GVHD will be assessed from screening through end of treatment (EOT) using the Mount Sinai Acute GHVD International Consortium (MAGIC) guidelines. Adverse events and SAEs will be assessed from the time of consent through 30 to 35 days after the EOT as per National Cancer Institute CTCAE v4.03. Subjects will be assessed for efficacy (including overall response, NRM, FFS, DOR, relapse rate, relapse-related mortality rates, and OS), safety (including AEs, SAEs, and clinical/laboratory assessments),

3.1. Control of Type I Error

No formal statistical tests will be performed. All confidence intervals (CIs) will be 95%.

3.2. Sample Size Considerations

Approximately 70 subjects are planned for the final analysis of the primary endpoint of ORR. A second-line treatment demonstrating a true ORR of 60% would be considered clinically meaningful. With the assumed true rate of 60%, a sample size of 70 subjects would provide > 90% probability to have a 95% CI with lower limit of \ge 40%.

An interim analysis will be conducted once 35 subjects complete the Day 28 visit. In this interim analysis, only futility will be assessed, and the trial will be terminated if the lower boundary is crossed.

A group sequential design method for 1 sample binary outcome data will be used to calculate the lower boundary of futility. The spending function of HSD(-4) will be used. For H0: p = 0.4, Ha: p = 0.6, and a 1-sided binomial test with alpha of 0.025, if ≤ 15 subjects respond at the time of the interim analysis, the study will be terminated. This will provide 70.03% probability for the response rate of 40% at the interim analysis.

If \geq 37 subjects respond at the time of final analysis, the study outcome will be considered positive. These assumptions will provide 89.88% power for the response rate of 60% in the final analysis with Type I error of 0.0189.

3.3. Schedule of Assessments

See Appendix C for assessment schedules for this study.

4. DATA HANDLING DEFINITIONS AND CONVENTIONS

4.1. Scheduled Study Evaluations and Study Periods

4.1.1. Day 1

Day 1 is the date of first dose of ruxolitinib. For patients who started corticosteroids before ruxolitinib, all study visits will be counted based on Day 1 of study.

4.1.2. Study Day

If a visit/reporting date is on or after Day 1, then the study day at the visit/reporting date will be calculated as follows:

Day # = [Visit/Reporting Date - Day 1 date + 1]

If the visit/reporting date is before Day 1, then the study day at the visit/reporting date will be calculated as follows:

Day # = [Visit/Reporting Date – Day 1 date]

A study day of -1 indicates 1 day before Day 1.

4.1.3. Baseline Value

Baseline is the last nonmissing measurement obtained on or before the day of the first administration of study drug. When scheduled assessments and unscheduled assessments occur on the same day and time of the assessment or first dose is not available, use the following convention to determine baseline:

- If both a scheduled and an unscheduled visit are available on the day of the first dose and the time is missing, use the scheduled assessment as baseline.
- If all scheduled assessments are missing on the day of the first dose and an unscheduled assessment is available, use the unscheduled assessment as baseline.

4.1.4. Last Available Value

The last available value is the last nonmissing measurement obtained after starting study drug.

4.2. Variable Definitions

4.2.1. Age

Subject age will be calculated as the integer part of the number of years from date of birth to the date of signing the informed consent form, using the following formula:

Age = integer part of (date of informed consent – date of birth + 1) / 365.25

4.2.2. Body Mass Index

Body mass index (BMI) will be calculated as follows:

BMI $(kg/m^2) = [weight (kg)] / [height (m)]^2$

4.2.3. Body Surface Area

Body surface area (BSA) will be calculated based on the Mosteller (1987) formula as follows:

BSA (m²) = {[weight (kg) × height (cm)] / 3600}^{$\frac{1}{2}$}

Sites will also record the BSA calculated per institutional standards.

4.2.4. Prior and Concomitant Medication

Prior medication is defined as any nonstudy medication started before the first dose of study drug.

Concomitant medication is defined as any nonstudy medication that is started accordingly:

- Before the date of first administration of study drug and is ongoing throughout the study or ends on/after the date of first study drug administration.
- On/after the date of first administration of study drug and is ongoing or ends during the course of study drug.

A prior medication could also be classified as "both prior and concomitant medication" if the end date is on or after first dose of study drug. In the listing, it will be indicated whether a medication is prior only, concomitant only, or both prior and concomitant.

For the purposes of analysis, all medications will be considered concomitant medications unless the medications can unequivocally be defined as not concomitant.

The start/stop dates recorded in the eCRF by the investigator and his or her research staff will be used to identify when a concomitant medication was taken during the study. Unresolved missing start dates will be handled as follows:

- For the starting date, impute as follows:
 - If the day is missing, then impute as the first day of the month.
 - If the month is missing, then impute as the first day of the year.
 - If the year is missing, then the medication will be considered both prior and concomitant.
- For the ending date, impute as follows:
 - If the day is missing, then impute as the last day of the month.
 - If the month is missing, then impute as the last day of the year.
 - If the year is missing, then the medication will be considered as ongoing until the end of the study.

5. STATISTICAL METHODOLOGY

5.1. General Methodology

Unless otherwise noted, SAS[®] software (SAS Institute Inc., Cary, NC; v9 or later) will be used for the generation of all tables, graphs, and statistical analyses. Descriptive summaries for continuous variables will include, but not be limited to, the number of observations, mean, standard deviation, median, minimum, and maximum. Descriptive summaries for categorical variables will include the number and percentage of subjects in each category.

5.2. Treatment Groups

This is a single-cohort study. Eligible subjects will begin treatment at ruxolitinib 5 mg BID; if hematologic parameters are stable and no treatment-related toxicity is observed after the first 3 days of treatment, the dose may be increased to 10 mg BID. Corticosteroids will be administered at a starting dose of 2.0 mg/kg per day (unless otherwise indicated) on Day 1 and will be tapered as appropriate.

5.3. Analysis Populations

5.3.1. Efficacy Evaluable Population

The efficacy evaluable population includes all subjects enrolled in the study. Demographics, baseline characteristics, subject disposition, and all efficacy analyses will be conducted using the efficacy evaluable population.

5.3.2. Safety Evaluable Population

The safety evaluable population includes all subjects enrolled in the study who received at least 1 dose of study drug. Treatment groups for this population will be determined according to the actual treatment that the subject received on Day 1. All safety analyses will be conducted using the safety evaluable population.

5.3.3. Pharmacokinetic Evaluable Population

The pharmacokinetic evaluable population includes subjects who receive at least 1 dose of study drug and provide at least 1 plasma sample (1 PK measurement) after study drug administration. The study pharmacokineticist will review data listings of study drug administration and sample records to identify subjects to be excluded from analyses of PK data.

6. BASELINE, EXPOSURE, AND DISPOSITION VARIABLES AND ANALYSES

6.1. Baseline and Demographics, Physical Characteristics, and Disease History

Demographic and baseline characteristics, disease history, and prior therapy will be summarized for the efficacy evaluable population and listed.

6.1.1. Demographics and Baseline Characteristics

Demographic and baseline characteristics include the following: age, sex, race, ethnicity, weight, height, BMI, BSA, and ECOG performance status.

6.1.2. Disease History

Cancer type, time since initial diagnosis, stage at diagnosis, current stage, disease histology, primary site of disease, mutation status, and site of metastatic disease at baseline will be summarized.

Time since diagnosis will be calculated as follows:

Time since diagnosis (years) = [Day 1 - date of diagnosis + 1] / 365.25

6.1.3. **Prior Therapy**

Number of subjects who received prior systemic therapy will be summarized for the efficacy evaluable population. Regimen name, component drugs, start and stop dates, purpose of the regimen, best response, reason for discontinuation, and date of relapse/progression will be listed.

Number of subjects who received prior radiation will be summarized for the efficacy evaluable population. Radiotherapy type, body site, start and stop dates, total dose, and best response will be listed.

Number of subjects who had prior surgery or surgical procedure for the malignancies under study will be summarized for the efficacy evaluable population. Date and description of the surgery/procedure will be listed.

6.1.4. Medical History

For subjects in the efficacy evaluable population, medical history will be summarized by system-organ class and preferred term and will be listed.

6.2. Disposition of Subjects

The number and percentage of subjects who were treated, discontinued study treatment with a primary reason for discontinuation, and discontinued from the study with a primary reason for withdrawal will be summarized for the efficacy evaluable population.

6.3. **Protocol Deviations**

Protocol deviations and violations collected on eCRF will be presented in the subject data listings.

6.4. Exposure

For subjects in the safety evaluable population, exposure to study drug (INCB018424) will be summarized descriptively as follows:

• Duration of treatment with study drug:

Duration of treatment (days) = Date of last dose of study drug – Date of first dose of study drug + 1

• Average daily dose of study drug:

Average daily dose of study drug (mg/day) = [total actual study drug dose taken (mg)] / [duration of treatment with study drug]

Summary for the planned exposure of corticosteroids will be provided.

6.5. Study Drug Compliance

For subjects in the safety evaluable population, overall compliance (%) for study drug (ruxolitinib) will be calculated for all subjects as follows:

Overall compliance (%) = $100 \times [\text{total dose actually taken (mg)}] / [\text{total prescribed dose (mg)}]$

The total prescribed dose is defined as the sum of the doses prescribed by the investigator accounting for dose modifications.

Compliance of study drug will be summarized descriptively and listed.

6.6. **Prior and Concomitant Medication**

Prior medications and concomitant medications will be coded using the WHO Drug Dictionary. For subjects in the safety population, the number and percentage of subjects with prior and concomitant medications will be summarized by WHO drug class and WHO drug term. In the data listing, each medication will be recorded as prior, concomitant, or both prior and concomitant.

7. EFFICACY

Planned tables, figures, and listings are provided in Appendix A. All efficacy analyses will be performed using the efficacy evaluable population.

7.1. General Considerations

Missing observations will be handled for specific endpoints as detailed in the sections addressing each analysis.

7.2. Efficacy Hypotheses

No formal statistical tests will be performed.

7.3. Analyses of the Efficacy Parameters

7.3.1. Primary Efficacy Analysis

Overall response rate at Day 28 is defined as the proportion of subjects demonstrating a CR, VGPR, or PR as per standard criteria (see Appendix B).

The proportion of responders will be estimated with 95% CIs for the efficacy evaluable population. Confidence intervals will be calculated based on the exact method for binomial distributions. Summary statistics will be provided.

Subjects who have missing response data at Day 28 (includes withdrawal or death before Day 28) will be considered nonresponders. The primary analysis will be conducted when all subjects have completed Day 28 response assessments or discontinued.

7.3.2. Secondary and Efficacy Analysis

7.3.2.1. Duration of Response

Duration of response at Month 6 is the key secondary endpoint. For responders, the DOR is defined as the difference of the end of response and the start of response for subjects who have at least 1 response measurement. The start of a response will be the first visit where the subject achieves PR or better based on response criteria in Appendix B (MAGIC guidelines). The end of response will be the first visit after GVHD progression based on response criteria in Appendix B or death. Duration of response will be assessed using the Kaplan-Meier method for subjects who achieve a response. Median duration and 95% CI will be estimated. Subjects who are still responding at the time of database lock or discontinuation will be right-censored at the

time of last valid response assessment. Six-month DOR will be assessed when all subjects complete the Day 180 visit.

In addition, 3-month DOR will be assessed. Three-month DOR is defined as the time from first response until GVHD progression or death, when all subjects complete the Day 84 visit. Duration of response will be assessed using the Kaplan-Meier method for subjects who achieve a response.

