APPENDIX B. MAGIC GUIDELINES FOR STAGING AND GRADING ACUTE GVHD

Stage	Skin (Active Erythema Only)	Liver (bilirubin)	Upper GI	Lower GI (stool output/day)
0	No active (erythematous) GVHD rash	< 2 mg/dL	No or intermittent nausea, vomiting, or anorexia	Adult: < 500 mL/day or < 3 episodes/day. Child: < 10 mL/kg per day or < 4 episodes/day.
1	Maculopapular rash < 25% BSA	2-3 mg/dL	Persistent nausea, vomiting, or anorexia	Adult: 500-999 mL/day or 3-4 episodes/day. Child: 10-19.9 mL/kg per day or 4-6 episodes/day.
2	Maculopapular rash 25%-50% BSA	3.1-6 mg/dL	_	Adult: 1000-1500 mL/day or 5-7 episodes/day. Child: 20-30 mL/kg per day or 7-10 episodes/day.
3	Maculopapular rash > 50% BSA	6.1-15 mg/dL	_	Adult: > 1500 mL/day or > 7 episodes/day. Child: > 30 mL/kg per day or > 10 episodes/day.
4	Generalized erythroderma (> 50%) with bullae	> 15 mg/dL	_	Severe abdominal pain with or without ileus or grossly bloody stool (regardless of stool volume).

Acute GVHD Staging and Grading, MAGIC Guidelines

Overall clinical grade (based on most severe target organ involvement):

Grade 0: No stage 1-4 of any organ.

Grade I: Stage 1-2 skin without liver, upper GI, or lower GI involvement.

Grade II: Stage 3 rash and/or stage 1 liver and/or stage 1 upper GI and/or stage 1 lower GI.

Grade III: Stage 2-3 liver and/or stage 2-3 lower GI, with stage 0-3 skin and/or stage 0-1 upper GI.

Grade IV: Stage 4 skin, liver, or lower GI involvement, with stage 0-1 upper GI.

Response Definitions:

GVHD response assessments will be made with respect to changes in the organ stage relative to Study Day 1.

- Complete response (CR) is defined as a score of 0 for the GVHD grading in all evaluable organs. For a response to be scored as CR at Day 28 or later, the participant must still be in CR on that day and have had no intervening additional therapy for an earlier progression, mixed response (MR), or no response (NR).
- Very good partial response (VGPR) is defined as follows:
 - Skin: No rash, or residual erythematous rash involving < 25% of the body surface, without bullae (residual faint erythema and hyperpigmentation do not count).
 - Liver: Total serum bilirubin concentration < 2 mg/dL or < 25% of baseline at enrollment.
 - Gut:
 - Tolerating food or enteral feeding.
 - Predominantly formed stools.
 - No overt gastrointestinal bleeding or abdominal cramping.
 - No more than occasional nausea or vomiting.

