- Partial response (PR) is defined as improvement in 1 stage in 1 or more organs involved with GVHD symptoms without progression in others. For a response to be scored as PR at Day 28 or later, the participant must still be in PR on that day and have had no intervening additional therapy for an earlier progression, MR, or NR.
- Mixed response is defined as improvement in 1 or more organs with deterioration in another organ manifesting symptoms of GVHD or development of symptoms of GVHD in a new organ.
- Progression of disease is defined as deterioration in at least 1 organ without any improvement in others.
- No response is defined as absence of any improvement or progression as defined. Subjects receiving secondary therapy (including need to re-escalate steroid dose to greater than the Day 1 dose), will be classified as nonresponders.

Source: CIBMTR 2009, Martin et al 2009, Harris et al 2016.

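### Duration of response ends only at Appendix B progression or death, so responders who fall to no response or mixed response have no event when response is lost, and new GVHD therapy is handled ambiguously

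*SAP*

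**What the plan says.** SAP 2.3.2 gives six-month DOR as the key secondary endpoint, "defined as the time from first response until GVHD progression or death". The Protocol synopsis, Section 2 and Section 9.4.2 use the same event list. SAP 7.3.2.1 makes it operational. Response starts at the first visit with PR or better, and "The end of response will be the first visit after GVHD progression based on response criteria in Appendix B or death". The section has one censoring rule: "Subjects who are still responding at the time of database lock or discontinuation will be right-censored at the" time of the last valid response assessment.

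The categories come from SAP Appendix B, which matches Protocol Appendix B:

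- Reference point: "GVHD response assessments will be made with respect to changes in the organ stage relative to Study Day 1".
- Progression: "Progression of disease is defined as deterioration in at least 1 organ without any improvement in others".
- Mixed response is a separate category: at least one organ better, with another worse or newly involved.
- No response: "No response is defined as absence of any improvement or progression as defined".
- New therapy: "Subjects receiving secondary therapy (including need to re-escalate steroid dose to greater than the Day 1 dose), will be classified as nonresponders".

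SAP Section 3 describes when treatment stops: "Subjects will receive study treatment until treatment failure (progression of GVHD, no response, or requiring additional systemic therapy), unacceptable toxicity, or death". Progression, no response and additional therapy are listed there as three different things.

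**The concern.** A six-month DOR is meant to show that responses last. Under Section 7.3.2.1 a response can be lost completely without any event being recorded, because two of the three non-responding categories in Appendix B are not on the event list. A later progression or death still counts, so the effect is that response runs on past its loss.

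New systemic GVHD therapy adds a second problem. Appendix B makes the subject a nonresponder without calling this progression. Protocol 5.4.2.3 does call it progression, but only during the ruxolitinib taper. Protocol 5.5.1 requires withdrawal from study treatment, so the subject might be censored at discontinuation, a word that Section 7.3.2.1 does not tie to treatment or to study. After new therapy, Protocol 6.4.3 plans contact about new therapy and survival only, so a later progression may never be staged.

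Two programmers could therefore derive different DOR results from the same data.

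**Working it through.** **No plan figure to reproduce.** The documents give no assumed rate, event count or precision for DOR. The check has two parts: classify example subjects by the written rules, then illustrate the size under stated assumptions.

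**1. Classification under Appendix B** (stages relative to Day 1; the examples are chosen so that VGPR does not arise at the loss)

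| Day 1 | Response | Later visit | Category | DOR event? |
|---|---|---|---|---|
| Skin 3 | Skin 0 (CR) | Skin 3 | NR | No |
| Skin 3 | Skin 0 (CR) | Skin 4 | Progression | Yes |
| Skin 3, lower GI 2 | 0 and 0 (CR) | Skin 4, lower GI 1 | MR; Grade IV by skin stage 4 | No |
| Skin 3, lower GI 2 | Skin 1, lower GI 0 (PR) | Skin 3, lower GI 2 | NR | No |

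A move from CR to PR with no organ worse than Day 1 is still a response and is not part of this point.

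**2. Handling after the loss.** The censoring rule can be read in two ways. If still responding means being in CR, VGPR or PR, an NR or MR subject is outside the rule and no other rule applies. If it means not yet having met the section's own end of response, the subject stays at risk as though response continued.

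**3. Size (assumptions, not document figures).** Let the reported 6-month DOR be 80%. Let f be the share of responders whose first event within 6 months is this loss, and g the share of those who then progress or die by Month 6.

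*Kept at risk, complete follow-up:* rate with losses counted = 0.80 − f(1 − g). For f = 0.10: g = 0 gives 0.70, g = 0.5 gives 0.75, g = 1 gives 0.80.

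*Censored at the loss, constant cause-specific hazards:* a = −ln(0.80) = 0.2231. Solve b/(a + b) × (1 − exp(−(a + b))) = f for b; the rate with losses counted is exp(−(a + b)). For f = 0.10: a + b = 0.3412, b = 0.1181, and 0.1181/0.3412 × (1 − 0.7109) = 0.100, so the rate is 71.1%.

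| f | Censored | At risk, g = 0 | At risk, g = 0.5 | At risk, g = 1 |
|---|---|---|---|---|
| 5% | 75.5% | 75% | 77.5% | 80% |
| 10% | 71.1% | 70% | 75% | 80% |
| 20% | 62.2% | 60% | 70% | 80% |
| 30% | 53.4% | 50% | 65% | not possible |

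In the last row, f × g cannot exceed 0.20, the share with a reported event. So g is at most 2/3 and the highest value is 0.80 − 0.30 × 1/3 = 70%.

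**4. Durations.** Response at Day 28, NR at Day 56, death at Day 168: kept at risk, DOR is 168 − 28 = 140 days. If NR ends response, it is 56 − 28 = 28 days. The status by Month 6 is the same and the duration differs by 112 days.

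**5. Scale.** With 37 responders (the success threshold) to 42 (60% of 70), one subject is 1/37 = 2.7 to 1/42 = 2.4 points, and 10% is about 4 subjects. The 95% half-width at 80% is 1.96 × √(0.8 × 0.2/n) = 12.9 points (n = 37) or 12.1 points (n = 42). Response at any visit starts DOR, so there may be more responders than this.

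**The case against.** The strongest reply is that progression or death is a declared event list, used consistently in both documents, and that DOR, ORR and FFS need not share events. That stands: the differing lists are not a contradiction, and SAP Section 3 is a treatment-stopping rule, not an endpoint definition. But a narrow event list must say what happens to subjects who have lost response, and Section 7.3.2.1 does not do so clearly.

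The losses are also partly visible elsewhere. ORR at Days 56 and 100 requires being in response on that day, FFS counts additional therapy, and the listings show response and DOR by subject. This limits the harm but does not correct the DOR estimate.

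The percentages are Kaplan-Meier rates at Month 6, whereas Section 7.3.2.1 names the median duration. In nearly every scenario above the median lies beyond Month 6 under either definition. At 5% to 10% loss the shift is also smaller than the confidence half-width. Both remarks are fair. The shift is nevertheless a bias in one direction, not sampling noise.

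Three stronger readings are tempting and are not supported:

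- That no censoring rule exists for these subjects. This is one reading; the other keeps them at risk. Response runs past its loss under that one too.
- That the wording on the first visit after progression delays every event to the next visit. It can equally mean the visit that shows progression, so no dating error is established.
- That these subjects never have an event. Later death counts, as does later progression if it is staged.

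**Conclusion.** The point holds. By the SAP's own definitions, a responder can return fully to Day 1 stages, or reach Grade IV with another organ still improved, without a DOR event at that loss. The handling of new systemic GVHD therapy is ambiguous. Where such losses occur, the reported 6-month DOR is too high. If every such subject later progresses or dies by Month 6 while kept at risk, the 6-month rate is unchanged and only the durations are too long.

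The size is unknown. The illustration of about 70% to 80% at 10% loss rests on an assumed reported rate of 80% and an assumed loss rate. The censored figures also assume constant hazards; they fit new-therapy subjects best, since no written rule clearly censors NR or MR subjects.

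A reader might infer that the trial's success claim is at risk. It is not: success depends on at least 37 responders at Day 28, and DOR is descriptive.

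**What to change.** In SAP 7.3.2.1, and in the matching wording in SAP 2.3.2 and the Protocol synopsis, Section 2 and Section 9.4.2, define the end of response as the earliest of:

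- (a) the first visit at which the subject is no longer in CR, VGPR or PR under Appendix B (progression, MR or NR);
- (b) the start of additional systemic GVHD therapy;
- (c) death.

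Date each event when it is first documented, that is, at the visit that shows it. State whether discontinuation means treatment or study. Censor subjects with no event at the last valid response assessment.

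Before (b) can be programmed, the passages on corticosteroid re-escalation or restart must be reconciled: Protocol 5.2.2.3, 5.4.2.3 and 5.5.1, and Appendix B. They differ on whether reaching the starting or Day 1 dose, exceeding it, or any restart counts. This review does not choose among them.

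Add two sensitivity analyses. The first keeps progression or death as the only events and states how NR, MR and new-therapy subjects are handled. The second does not count a single NR or MR visit followed by regained response without new therapy, since Protocol 5.2.2.3 and 5.4.2.2 allow a flare to be managed on study.

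Cost: a Protocol amendment to the endpoint wording, SAP text, derivation programming and two tables. No new data are needed, because organ staging and new GVHD therapy are already collected. Reported DOR may be shorter.
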